Adverse Event Assessments	X	X	AEs during the survival follow up visits considered study drug-related should be followed until resolution, stabilization, or returned to baseline.
Laboratory Tests	X		CBC w/differential, total protein, ALT, AST, total bilirubin, direct bilirubin (reflex testing when total bilirubin is elevated), alkaline phosphatase, BUN or serum urea level, uric acid, creatinine, albumin, Ca, Mg, Na, K, P, Cl, LDH, glucose, amylase, lipase, TSH (Free T4 and Free T3 reflex testing if TSH result abnormal).
Pregnancy Test (WOCBP Only)	X		Serum or urine
Review of Concomitant Medications	X		
PK Samples	X		See section 5.5
Immunogenicity blood sample	X		See section 5.5
Survival Status			
Subject Status	X	X	Every 3 months, may be accomplished by visit, phone contact or email, to assess subsequent anti-cancer therapy
Efficacy Assessments			
Tumor Assessment		See Notes	
Only for subjects without progression on study therapy and even if they receive subsequent treatment.
 
Every 6 weeks (<math>\pm</math> 1 wk) from first dose for the first 24 weeks, then every 12 wks (<math>\pm</math> 1 wk) until disease progression or treatment is discontinued (whichever occurs later).
 
CT chest, CT/MRI abdomen, pelvis and all known sites of disease. Use same imaging method as was used at screening/baseline.
 
Subjects with a history of brain metastasis should have surveillance MRI approximately every 12 weeks, or sooner if clinically indicated

Table 5.1-5: Follow-up Assessments (CA212115) - All Subjects			
Procedure	Follow Up,a Visits 1 and 2	Survival,b Follow up Visits	Notes
Outcomes Research Assessments			
EQ-5D	X	X	The EQ-5D can be done via a phone contact when a clinic visit is not feasible (ie, follow up scans are being done at another facility or department) in order to not miss the assessment.
Cancer-specific questionnaire* LCSS (SCLC) EORTC-QLQ-C30 (PAC)	X	X	*Only for Stage 2 Randomized study subjects

a Follow-up visit 1 (FU1) = 35 days ( $\pm$  7 days) from the last dose or coincide with the date of discontinuation ( $\pm$  7 days) if date of discontinuation is greater than 42 days after last dose, Follow-up visit 2 (FU2) = 80 days ( $\pm$  7 days) from follow-up visit 1

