b Survival visits = every 3 months from FU2. Regardless of any subsequent treatment, all subjects will remain on study follow-up for disease progression and survival assessment.

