### **6.1.1 Serious Adverse Event Collection and Reporting**

Sections 5.6.1 and 5.6.2 in the Investigator Brochure (IB) represent the Reference Safety Information to determine expectedness of serious adverse events for expedited reporting. Following the subject's written consent to participate in the study, all SAEs, whether related or not related to study drug, must be collected, including those thought to be associated with protocol-specified procedures. All SAEs must be collected that occur during the screening period and within 100 days of discontinuation of dosing. Subjects who are randomized and never treated with study drug must have SAEs collected for 30 days from the date of randomization. If applicable, SAEs must be collected that relate to any later protocol-specified procedure (eg, a follow-up skin biopsy).

The investigator must report any SAE that occurs after these time periods and that is believed to be related to study drug or protocol-specified procedure.

An SAE report must be completed for any event where doubt exists regarding its seriousness.

If the investigator believes that an SAE is not related to study drug, but is potentially related to the conditions of the study (such as withdrawal of previous therapy or a complication of a study procedure), the relationship must be specified in the narrative section of the SAE Report Form.

SAEs, whether related or not related to study drug, and pregnancies must be reported to BMS (or designee) within 24 hours of awareness of the event. SAEs must be recorded on the SAE Report Form; pregnancies on a Pregnancy Surveillance Form (electronic or paper forms). The preferred method for SAE data reporting collection is through the eCRF. The paper SAE/pregnancy surveillance forms are only intended as a back-up option when the eCRF system is not functioning. In this case, the paper forms are to be transmitted via email or confirmed facsimile (fax) transmission to:

**SAE Email Address:** Refer to Contact Information list.

**SAE Facsimile Number:** Refer to Contact Information list.

For studies capturing SAEs through electronic data capture (EDC), electronic submission is the required method for reporting. The paper forms should be used and submitted immediately, only in the event the electronic system is unavailable for transmission. When paper forms are used, the original paper forms are to remain on site.

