4.2.1 Select Adverse Events

The select Adverse Events (select AEs) consist of a list of preferred terms grouped by specific category that are of relevance for understanding the risks of immune therapies such as nivolumab. To date, 7 categories of select AEs have been identified see Table 4.2.1-1.

Table 4.2.1-1: Select Adverse Events

Category	Subcategory
Endocrine Adverse Events	Adrenal Disorder
	Diabetes
	Pituitary Disorder
	Thyroid Disorder
Hypersensitivity/Infusion Reactions	
Gastrointestinal Adverse Events	
Hepatic Adverse Events	
Pulmonary Adverse Events	
Renal Adverse Events	
Skin Adverse Events	

AEs that may differ from or be more severe than AEs caused by non-immunotherapies and AEs whose early recognition and management may mitigate severe toxicity are included as select AEs. The select AEs and the categories are defined by the Sponsor and the list that is the most current at the time of analysis will be used. Changes may be made to this list with each new version of the Medical Dictionary for Regulatory Activities (MedDRA), prior to database lock. Categories of select AEs may include subcategories (e.g. adrenal disorders, diabetes, pituitary disorders, and thyroid disorders are subcategories of the endocrine event category). Other categories could be created during the conduct of the study. If so, similar table/listing will be produced for these

additional categories. Similarly, some category can be removed or regrouped and corresponding table/listing will be updated accordingly.

The analysis of select adverse events will be conducted using the 30-day safety window.

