6.1.2 Post Baseline Period

- On-treatment AEs will be defined as AEs with an onset date on or after the first day of treatment.
- For infusion related events, on-treatment will be defined as AEs with an onset date and time on or after the first day and time of treatment.
- For all other evaluations (ECOG, laboratory data, ECGs, vital signs, etc.) on-treatment will be defined as evaluations taken after the first day of treatment.
- If a subject is still on study treatment, any AE/evaluation post baseline is considered as on-treatment. For subjects off study treatment, AEs/evaluations will be counted as on-treatment if the event occurred within 30 days or 100 days (depending on the analysis) after the last dose of ulocuplumab or nivolumab, whichever is later.
- Late-emergent drug-related AEs will be defined as drug-related AEs with an onset date greater than 100 days after the last dose of study treatment in subjects who are off study treatment.

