7.6.6 All Adverse Events

For AEs the following will be summarized:

- Overall summary of any AEs by worst CTC grade (grade 1, 2, 3, 4, 5, unknown) presented by SOC/PT,
- Overall summary of any AEs by worst CTC grade (any grade, grade 3-4, grade 5) presented by SOC/PT,
- Overall summary of drug-related AEs by worst CTC grade (any grade, grade 3-4, grade 5) presented by SOC/PT,
- Overall summary of any non-serious AEs presented by SOC/PT. For the Dose Evaluation Phase, only the population of All Dose Evaluation Treated Subjects will be used.
- Overall summary of late-emergent drug-related AEs by worst CTC grade (grade 1, 2, 3, 4, 5, unknown) presented by SOC/PT,
- Overall summary of any AEs that required IMM by worst CTC grade (any grade, grade 3-4, grade 5) presented by SOC/PT.

The analyses will be conducted using the 100 days safety window.

Listing of AEs and listing of AEs requiring concomitant IMM will be provided.

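### SAP 7.6.6 puts the late-emergent AE summary under a 100-day window that excludes every late-emergent event (minor); separately, the select-AE incidence tables would benefit from a 100-day version

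*SAP*

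**What the plan says.** **Late-emergent events.** SAP 7.6.6 (All Adverse Events) lists six summaries, the fifth being "Overall summary of late-emergent drug-related AEs by worst CTC grade". After the list comes a single sentence with no exception: "The analyses will be conducted using the 100 days safety window". SAP 6.1.2 (Post Baseline Period) explains the window. Once a subject has stopped dosing, the rule is: "AEs/evaluations will be counted as on-treatment if the event occurred within 30 days or 100 days (depending on the analysis) after the last dose", taking the later of the two drugs' last doses. The same section says "Late-emergent drug-related AEs will be defined as drug-related AEs with an onset date greater than 100 days after the last dose", in subjects who are off study treatment.

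**Select AEs.** SAP 4.2.1 states: "The analysis of select adverse events will be conducted using the 30-day safety window". Sections 7.6.8.1 (incidence) and 7.6.8.2 (immune-modulating medication) repeat the 30-day window and say it is the only one. Section 7.6.11 also uses 30 days. It covers two things: total and exposure-adjusted counts of AEs in general, and the frequency of unique select AEs.

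**Sections that count to 100 days.** These are SAP 7.6.3 (SAEs), 7.6.4 (AEs leading to discontinuation), 7.6.6 (all AEs) and 7.6.9 (immune-mediated AEs, IMAEs). Protocol 8.4.3 also counts AEs as on-study to 100 days after the later last dose, and asks for them by system organ class and preferred term. It does not mention select AEs.

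**The concern.** Safety and tolerability is a secondary objective. In the visible text, the late-emergent summary is the only planned AE incidence table for drug-related events starting after day 100. If its stated window excludes every event it is defined to contain, a programmer must either override a written rule or produce an empty table. A reader of the report could take an empty table to mean that no late drug-related toxicity occurred.

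For select AEs, the SAP says that these categories matter for understanding the risks of immune therapies, yet their incidence tables stop earlier than the SAE and discontinuation tables. A serious select AE starting 60 days after the last dose is counted in the SAE table but not in the serious select-AE table.

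**Working it through.** No figure in the plan is in dispute, so the check sets the rules side by side and then sizes the consequence.

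**1. Overlap of the 7.6.6 window and the 6.1.2 definition.** Let d be days from last dose to onset in a subject off treatment.

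- Window: d ≤ 100.
- Late-emergent: d > 100.
- Days meeting both: 0.
- Without the window, the summary starts at d = 101.
- Summaries affected: 1 of 6.

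**2. Can such events reach the database?** Yes, by two routes.

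- Protocol 6.1.1 collects SAEs to 100 days after dosing stops, and then adds: "The investigator must report any SAE that occurs after these time periods and that is believed to be related to study drug" or to a protocol-specified procedure.
- Protocol Table 5.1-5 assesses AEs at survival visits: "AEs during the survival follow up visits considered study drug-related should be followed until resolution, stabilization, or returned to baseline". The timing is given as "Survival visits = every 3 months from FU2". Follow-up visit 1 (FU1) is 35 ± 7 days from last dose, so no earlier than 35 − 7 = day 28. FU2 is 80 ± 7 days after FU1, so no earlier than 28 + 80 − 7 = day 101. Survival visits come after that. The alternative FU1 rule, for subjects who discontinue more than 42 days after last dose, only moves these dates later.

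**3. Gap in the select-AE tables.** Days inside the 100-day window but outside the 30-day window are 31 to 100, which is 70 days. All six incidence summaries in 7.6.8.1 use 30 days and none has a 100-day version. A select AE starting on one of those days appears as follows:

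| Output | Window | Included? | Grouped by select-AE category? |
|---|---|---|---|
| SOC/PT tables (7.6.3, 7.6.4, 7.6.6) | 100 days | Yes, where the event qualifies | No |
| IMAE output (7.6.9): listing and medication table | 100 days | Only if it is an IMAE event and, except for endocrine events, was treated with immunosuppressive medication (4.2.2) | No select-AE incidence |
| Select-AE incidence (7.6.8.1) | 30 days | No | Yes |
| Select-AE listing (7.6.8.1) | Not stated | Unclear | A listing, not an incidence table |

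**4. Size for one affected subject.** Safety tables for the Dose Evaluation Phase use All Dose Evaluation Treated Subjects by cohort, which includes DLT-period subjects (SAP 6.3 and 7.6). Planned cohorts are 19 (SCLC) and 21 (PAC). I assume 0 to 6 DLT-period subjects of the same tumor type at the same dose, giving n = 19-25 and 21-27. A subject whose only event in a category starts on days 31-100 shifts that category's incidence by 1/n:

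- 1/19 = 5.3%; 1/25 = 4.0%
- 1/21 = 4.8%; 1/27 = 3.7%
- Cohort closed during the DLT period, n = 6: 1/6 = 16.7%

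The last case is relevant. SAP section 2 reports more than two DLTs at DL1 and the opening of DL-1, and protocol 3.1.1 pauses enrollment of a DLT cohort at six subjects.

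For scale, exact (Clopper-Pearson) 95% intervals are 0/19: 0-17.6% against 1/19: 0.1-26.0%, and 0/27: 0-12.8% against 1/27: 0.1-19.0%. These illustrate the effect of one subject. They do not show that any such subject exists.

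**The case against.** **On the late-emergent summary.** The definition in 6.1.2 is specific and complete. The closing sentence of 7.6.6 can be read as merely choosing between the 30-day and 100-day cut-offs for the section, and the late-emergent definition starts from that same 100-day cut-off. The SAP also leaves conventions and the list of outputs to a Data Presentation Plan, which is not among the documents and may settle the matter. This stands as a reason to call the point minor. It does not make the sentence correct: a general rule that contradicts one of the items it governs should carry an exception. A reader might infer that late drug-related toxicity will in fact be lost or reported as absent. The documents do not support that, because the definition shows what is meant and the events are collected.

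**On select AEs.** The 30-day window is deliberate, consistently stated and allowed by 6.1.2. A reader might infer that it breaches protocol 8.4.3. It does not: that section lists the tabulations it requires, select-AE categories are not among them, and SAP 7.6.3, 7.6.4 and 7.6.6 provide the main ones at 100 days. Nor would it be right to say that later select AEs go unreported, since they reach the SOC/PT tables and the AE listings. It would also be too broad to say that every all-AE output uses 100 days, because 7.6.11 gives its total and exposure-adjusted AE counts at 30 days. What remains is narrower: pooling preferred terms by category is the purpose of the select-AE tables, and no planned table does this to day 100. Category counts could be built by hand from the preferred-term list and the AE listings.

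**Conclusion.** Two findings of different kinds.

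(1) SAP 7.6.6 is wrong as written for one of its six summaries. The overlap between its window and the late-emergent definition is zero days. The error is minor because the intent can be recovered from 6.1.2.

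(2) The 30-day-only select-AE incidence tables are neither an error nor a protocol breach. A 100-day version is a worthwhile, low-cost improvement, because it would match the 100-day count in protocol 8.4.3 and the IMAE output does not supply it.

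One affected subject is worth about 4-5 percentage points in a completed cohort, given the assumed 0-6 DLT-period subjects, and about 17 points in a cohort of six. The number of affected subjects cannot be computed from the documents. No primary endpoint or decision rule is touched by either finding.

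**What to change.** (1) In SAP 7.6.6, add a clause saying that the late-emergent summary follows the 6.1.2 definition (onset after day 100, subject off treatment) and is exempt from the window sentence. The cost is one clause.

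(2) Keep the 30-day select-AE tables and add 100-day versions of the 7.6.8.1 incidence tables. The cost is six summaries rerun over ten groupings: six non-endocrine categories plus four endocrine subcategories. No new data are needed, because AEs and SAEs are already analyzed to day 100. The downside is more tables in small cohorts, and later events may be confounded by subsequent therapy; showing both windows side by side helps to make that visible. Extending 7.6.8.2 and 7.6.11 in the same way is optional. While 7.6.8.1 is open, it would help to state which window applies to the select-AE listing.

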7.6.7 Infusion-related Events

For AEs reported as “Infusion-related Event = Yes” on the AE/SAE CRF page, a by-subject listing will be provided:

This analysis will be conducted using the 30-day safety window only.

7.6.8 Select Adverse Events

7.6.8.1 Incidence of Select Adverse Events

For select AEs (see categories and subcategories definition in [Table 4.2.1-1](#)) each of the following analysis will be repeated for each category of select AE (excluding the endocrine event category). Analyses of the endocrine event category will be presented separately by subcategories.

- Overall summary of any select AEs by worst CTC grade presented by Category or Subcategory (any grade, grade 3-4, grade 5),
- Overall summary of drug-related select AEs by worst CTC grade presented by Category or Subcategory (any grade, grade 3-4, grade 5),
- Overall summary of any serious select AEs by worst CTC grade presented by Category or Subcategory (any grade, grade 3-4, grade 5),
- Overall summary of drug-related serious select AEs by worst CTC grade presented by Category or Subcategory (any grade, grade 3-4, grade 5),
- Overall summary of any select AEs leading to discontinuation by worst CTC grade presented by Category or Subcategory (any grade, grade 3-4, grade 5),
- Overall summary of drug-related select AEs leading to discontinuation by worst CTC grade presented by Category or Subcategory (any grade, grade 3-4, grade 5).

These analyses will be conducted using the 30-day safety window only.

The list of PTs used for analysis will be provided. Listing of select AEs (any, serious and leading to discontinuation) will be provided.

7.6.8.2 IMM Received for Management of Select Adverse Events

Analysis of concomitant IMM received for management of any select AE among subjects who experienced at least one select AE will be provided separately for each category of select AEs (including the endocrine event category, as a whole) for the following specific events:

- Any grade select AEs,
- Any grade drug-related select AEs,

For these analyses, the following will be provided:

- Concomitant IMM received classified by anatomic class, therapeutic class and generic name,
- Number of subjects who received IMM,
- Total duration of IMM (in weeks, descriptive statistics),
- Number of subjects who received corticosteroid at a dose ≥ 40 mg prednisone or equivalent,
- Duration of corticosteroid at a dose ≥ 40 mg or equivalent (in weeks, descriptive statistics),
- Initial dose (mg/kg) of corticosteroid at a dose ≥ 40 mg prednisone or equivalent (descriptive statistics),
- Number of subjects who underwent corticosteroid taper,
- Duration of corticosteroid taper (in weeks, descriptive statistics).

The analyses will be conducted using the 30-day safety window only.

7.6.9 Immune-mediated Adverse Events

For IMAEs (see categories and PT definition in [Section 4.2.2](#)) a listing will be provided. Immune-modulating medications used for IMAE management will be tabulated. The list of PTs used for analysis will be provided.

These analyses will be conducted using the 100-day safety window only.

7.6.10 Other Events of Special Interest

For other events of special interest (see categories definition in [Section 4.2.3](#)) a listing will be provided. Immune-modulating medications used for other events of special interest will be tabulated. The list of PTs used for analysis will be provided.

7.6.11 Multiple Adverse Events

For multiple adverse events, the following will be summarized:

- Total number and exposure adjusted AEs summary,
- Frequency of unique adverse events summary (for select AEs only and presented for each category, including the endocrine event category, as a whole),

The analyses will be conducted using the 30-day safety window.

Listing displaying the unique instances of all AEs, i.e., after duplicates have been eliminated and overlapping and contiguous occurrences of the same event (i.e. same PT) have been collapsed will be provided. No formal comparisons will be made between cohorts.

7.6.12 Clinical Laboratory Evaluations

7.6.12.1 Hematology, Serum Chemistry, and Electrolytes

Thrombocytopenia will mainly be examined using laboratory data. Analyses on hematology, serum chemistry, and electrolytes will consist of the followings:

- Worst CTC grade on-treatment per subject,
- Shift table of worst on-treatment CTC grade compared to baseline CTC grade per subject.

For each analysis, the following laboratory tests will be summarized:

- Hematology: hemoglobin (HB), platelets, white blood counts (WBC), absolute neutrophils count (ANC) and absolute lymphocyte count (LYMPA).
- Serum chemistry: alanine aminotransferase (ALT), aspartate aminotransferase (AST), alkaline phosphatase (ALP), total bilirubin and creatinine.

- Electrolytes: sodium (high and low), potassium (high and low), calcium (high and low), magnesium (high and low).
- Other: amylase (AMYL) and lipase (LIPA and LIPAC, lipase by colorimetric assay).

The analyses will be conducted using the 100-day safety window.

Listing of these laboratory parameters will be provided.

7.6.12.2 Abnormal Hepatic Function Tests

The number of subjects with the following abnormalities vs. lower limit of normal (LLN) or vs. upper limit of normal (ULN) will be summarized:

- ALT or AST > 3 x ULN, > 5 x ULN, > 10 x ULN and > 20 x ULN.
- Total bilirubin > 2 x ULN.
- Concurrent (within 1 day) ALT or AST > 3 x ULN and total bilirubin > 2 x ULN.
- Concurrent (within 30 days) ALT or AST > 3 x ULN and total bilirubin > 2 x ULN.

The analyses will be conducted using the 100-day safety window.

Listing of these specific abnormalities will be provided.

7.6.12.3 Abnormal Thyroid Function Tests

The number of subjects with the following laboratory abnormalities will be summarized:

- Thyroid specific test (TSH) > ULN:
 - Any,
 - With TSH ≤ ULN at baseline,
 - With at least one FT3/FT4 test value < LLN,
 - With all other FT3/FT4 test values ≥ LLN,
 - With FT3/FT4 test missing.
- Thyroid specific test (TSH) < LLN:
 - Any,
 - With TSH ≥ LLN at baseline,
 - With at least one FT3/FT4 test value > ULN,
 - With all other FT3/FT4 test values ≤ ULN,
 - With FT3/FT4 test missing.

The analyses will be conducted using the 100-day safety window.

Listing of these specific abnormalities will be provided.

[Redacted]

[Redacted]

[Redacted]

[Redacted]

[Redacted]

[Redacted]

[Redacted]

[Redacted]

[Redacted]

[Redacted]

[Redacted]

[Redacted]

[Redacted]

[Redacted]

[Redacted]

[Redacted]

[Redacted]

[Redacted]

[Redacted]

[Redacted]

[Redacted]

[Redacted]

[Redacted]

[REDACTED]

[REDACTED]

[REDACTED]

[REDACTED]

[REDACTED]

[REDACTED]

[REDACTED]

[REDACTED]

[REDACTED]

[REDACTED]

[REDACTED]

[REDACTED]

[REDACTED]

[REDACTED]

[REDACTED]

[REDACTED]

[REDACTED]

[REDACTED]

